## 5.6.2 Cautionary Therapy

CCI Based on the anticipated plasma concentrations of AT-281 and their transient nature, no clinically relevant drug-drug interaction (DDI) is anticipated.

### CYP3A4 based interaction

CYP3A4- sensitive substrates, in particular, those with a narrow therapeutic index (NTI), should be used with caution. Common examples of CYP3A4- sensitive substrates with NTI include aminophylline, warfarin, methotrexate and amitriptyline. A list of CYP3A4 substrates with NTI is available at: <https://go.drugbank.com/categories/DBCAT004028>.

The investigator or designee should consider substituting or stopping CYP3A4 substrates with NTI during study treatment and resuming them approximately 12 hours after the final dose of AT-752. In the event that the CYP3A4 substrate with NTI cannot be safely discontinued or substituted, the patient must not be enrolled.

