#### **4.2 EXCLUSION CRITERIA**

A patient who meets any of the following criteria will be excluded from participation in this study:

1. Pregnant at screening or plans to become pregnant within 90 days of screening
2. Female patient who is breastfeeding or plans to breastfeed during the study period
3. Has previously received any investigational or approved vaccine for dengue
4. Previous history of HIV, active chronic hepatitis B infection, or current hepatitis C infection (from medical history)
5. Use of any antiviral drug within 30 days or within 5 half-lives (whichever is longer) of the active drug or metabolite (for long-acting antivirals) of screening
6. Currently enrolled in or plans to participate in another clinical trial with an investigational agent or device that will be received during the study-reporting period
7. Exposure to another investigational agent within 30 days or 5 half-lives, whichever is longer, prior to study drug administration
8. Concomitant use of herbal or natural supplements or grapefruit juice (e.g. St. John's Wort, echinacea, milk thistle) or grapefruit juice. These should be discontinued at screening if the investigator feels that they can be safely discontinued or substituted for the duration of the study.
9. Patients with chronic medical conditions that put them at risk for severe dengue, including uncontrolled diabetes mellitus, severe asthma requiring oral steroids, and admission to the hospital in the previous 6 months for cardiac disease
10. Current use of anticoagulant or antiplatelet drugs or documented medical history of bleeding disorders
11. Malabsorption syndrome or other conditions that would interfere with enteral absorption
12. Immunocompromised due to use of immunosuppressive drugs including systemic corticosteroids (inhaled or topical corticosteroids are allowed) or any current disease or immunocompromised due to any current disease or condition
13. Use of P-glycoprotein (P-gp) inducers and inhibitors as described in [Section 5.6.1](#). *Note: hydroxychloroquine and amiodarone are prohibited within 3 months prior to screening and during the study.*

14. Evidence of severe dengue disease including:

- Severe plasma leakage leading to shock or fluid accumulation with respiratory distress
- Severe bleeding (including any subjects with hemoglobin levels <13.0g/dL in males and <11.0g/dL in females)

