### 5.6.1 Prohibited Therapy

Use of the following therapies is prohibited from Screening/Day 1 (unless otherwise specified below) until study completion or early termination, as described below:

- Any previously received investigational or approved vaccine for dengue
- Any antiviral drug within 30 days or within 5 half-lives (whichever is longer) of the active drug or metabolite (for long-acting antivirals)
- Exposure to another investigational agent within 30 days or 5 half-lives, whichever is longer, prior to study drug administration
- Concomitant use of herbal or natural supplements or grapefruit juice (e.g. St. John's Wort, echinacea, milk thistle). A washout period of at least 7 days must be observed prior to study drug dosing, if the investigator feels that they can be safely discontinued or substituted for the duration of the study
- Use of anticoagulant or antiplatelet drugs
- Use of medications for treatment of inflammatory bowel disease
- Use of immunosuppressive drugs including systemic corticosteroids (defined as prednisone equivalent of > 10 mg/day for > 2 weeks; inhaled or topical corticosteroids are allowed)
- Use of P-glycoprotein (P-gp) inducers and inhibitors as described below.
  - Note: hydroxychloroquine and amiodarone are prohibited within 3 months prior to screening and during the study.

CCI

P-gp inhibitors should be safely discontinued or substituted approximately 12 hours prior to the first dose of AT-752. Patients may resume use of the discontinued or substituted P-gp inhibitor approximately 12 hours after the final dose of AT-527. If the P-gp inhibitors cannot be safely discontinued or substituted, the subject must not be enrolled.

Note: Hydroxychloroquine and amiodarone are prohibited within 3 months prior to screening and during the study.

For a list of P-gp inhibitors, refer to <https://go.drugbank.com/categories/DBCAT002667>

The following P-gp inducers are prohibited:

- Anticonvulsants: carbamazepine, phenytoin, phenobarbital, oxcarbazepine
- Rifamycins: rifabutin, rifampin, rifapentine
- St. John's Wort

CCI

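### Protocol section 5.6.2 treats warfarin as a drug for caution, or for pausing and early restart, while exclusion 10 and section 5.6.1 bar anticoagulants; a related restart rule names the wrong study drug

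*Protocol*

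**What the plan says.** The instructions sit in three places in the protocol.

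- **Section 5.6.2 (CYP3A4 based interaction).** Sensitive CYP3A4 substrates, particularly those with a narrow therapeutic index (NTI), "should be used with caution". The examples follow: "Common examples of CYP3A4- sensitive substrates with NTI include aminophylline, warfarin, methotrexate and amitriptyline". The investigator "should consider substituting or stopping CYP3A4 substrates with NTI during study treatment and resuming them approximately 12 hours after the final dose of AT-752". The paragraph closes with a bar on entry: "In the event that the CYP3A4 substrate with NTI cannot be safely discontinued or substituted, the patient must not be enrolled".
- **Section 4.2, exclusion 10 (repeated in the synopsis).** This rules out "Current use of anticoagulant or antiplatelet drugs or documented medical history of bleeding disorders".
- **Section 5.6.1.** The list of therapies prohibited from Screening/Day 1 to study completion or early termination, unless otherwise specified below, includes "Use of anticoagulant or antiplatelet drugs". It also includes immunosuppressive drugs.

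Section 5.6.1 has its own stop-and-restart rule for P-gp inhibitors. The stop is timed from the first dose of AT-752, but the restart reads: "Patients may resume use of the discontinued or substituted P-gp inhibitor approximately 12 hours after the final dose of AT-527".

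**The concern.** Warfarin appears as an example of a drug to be handled with caution, and belongs to a class that the same protocol excludes at entry and prohibits throughout follow-up. An investigator who reads section 5.6.2 alone would conclude that a restart shortly after the last dose is acceptable. One who reads section 5.6.1 would conclude that it is prohibited until the final visit.

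Two things are at stake. The first is consistent handling of an anticoagulant in a trial that treats bleeding as an entry concern: exclusion 10 covers bleeding disorders, exclusion 14 severe bleeding, and exclusion 17 platelets below 80,000/mm³. The second is how deviations are classified. SAP section 4.3 limits the per-protocol population to subjects without a major protocol violation that affects safety or data quality. Whether a given use of warfarin is a violation at all depends on which section is followed.

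Two neighbouring texts have related problems. The final sentence of the section 5.6.2 paragraph works as an eligibility criterion but is not among the criteria. The P-gp restart rule is tied to a drug that is not given in this trial.

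**Working it through.** No sample size, power or error rate is involved. The check is a comparison of texts plus a count of days.

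**1. Warfarin, stage by stage**

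| Stage | Section 5.6.2 | Exclusion 10 and section 5.6.1 |
|---|---|---|
| Entry | Not enrolled only if the drug cannot be safely stopped or substituted | Current anticoagulant use excluded |
| During treatment | Caution; consider stopping or substituting | Prohibited |
| After the last dose | Restart about 12 h later | Prohibited until study completion or early termination |

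The three rows differ in force. At entry the two columns can both be applied, because exclusion 10 is simply the stricter condition. The second and third rows give different instructions for the same drug.

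**2. Length of the restart conflict**

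Inputs:
- Last dose on Day 5 or Day 6, depending on when dosing starts on Day 1 (synopsis, estimated study duration; Tables 3-2 to 3-6).
- Restart about 12 h after the last dose (section 5.6.2).
- Final visit on Day 28 ± 3 days, that is Day 25 to Day 31 (section 3).

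Restart day: a last dose on the evening of Day 5, plus 12 h, gives Day 6. A last dose on Day 6, plus 12 h, gives late Day 6 or early Day 7.

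Conflict = day of final visit − restart day:
- nominal: 28 − 7 = 21 to 28 − 6 = 22 days;
- shortest with the window: 25 − 7 = 18 days;
- longest with the window: 31 − 6 = 25 days.

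**3. Whether any text resolves it**

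The opening of section 5.6.1 allows for exceptions specified below it. Nothing visible below it in that section exempts warfarin, and section 5.6.2 neither presents itself as an exception nor refers to exclusion 10 or to the section 5.6.1 list. Where the protocol wants a route for stopping a drug and entering the trial, it states one: exclusion 8 does so for supplements, and section 5.6.1 for P-gp inhibitors. The anticoagulant entries have none. Section 5.6 says how the investigator and sponsor should proceed once a prohibited drug has been taken, but not whether this drug is prohibited.

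**4. Methotrexate**

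Section 5.6.1 prohibits immunosuppressive drugs. Exclusion 12 is narrower: it concerns patients who are immunocompromised because of such drugs. Neither document classes methotrexate as an immunosuppressant. The conflict with section 5.6.1 is therefore conditional on the sponsor classing it as one.

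**5. The enrolment bar in section 5.6.2**

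None of the 18 exclusions in section 4.2 or the synopsis mentions CYP3A4 or NTI drugs. Exclusion 13 points to section 5.6.1 for P-gp drugs only, and exclusion 18 concerns a disease or condition. An eligibility check against either list would not find this bar.

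**6. AT-527**

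The restart clause for P-gp inhibitors is timed from the final dose of AT-527. The study drug is AT-752, so as written the clause has no reference time in this trial.

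**The case against.** The strongest reply concerns enrolment. A reader might infer that section 5.6.2 lets sites enrol patients who are taking an anticoagulant. The documents do not support that. Meeting any one exclusion is enough to keep a patient out, SAP section 4.2 randomizes only subjects who meet none, and protocol section 10.2.4.2 does not allow eligibility waivers. The only enrolment sentence in section 5.6.2 adds a restriction; it lifts none. This part of the reply stands in full.

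It also narrows the restart conflict. A patient must be eligible before the question of restarting arises, so the early-restart wording reaches mainly someone who stopped before screening and is judged not to be a current user. For that patient, however, a restart about 12 h after the last dose would still breach section 5.6.1. The group is smaller, but the contradiction remains.

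A reader might also say that two of the four named examples are barred elsewhere. Only warfarin is a firm case. Methotrexate depends on a classification that the documents do not make, and exclusion 12 does not ban the drug as such.

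Redactions are a fair caution. Text is blacked out within and at the end of section 5.6.1 and at the opening of section 5.6.2, where a statement of precedence could sit. The conclusion therefore covers visible text only.

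The shift in section 5.6.2 from considering a stop to forbidding enrolment can be read as successive steps, so calling it a flat self-contradiction would go too far. The absence of the bar from both exclusion lists is still a gap. The intended meaning of the AT-527 reference can be guessed from the sentence before it, but it is an operative instruction and should not need guessing.

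**Conclusion.** The inconsistency is real and limited. For warfarin, section 5.6.2 conflicts with section 5.6.1 on use during treatment, and on restart for about 21 to 22 days (18 to 25 with the visit window). Its wording also sits uneasily with exclusion 10, although exclusion 10 should decide entry. No visible text says which section governs.

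The consequence is conflicting instructions during treatment and follow-up, and uncertainty over whether such use is a deviation that could bear on per-protocol membership. Membership of the mITT population used for the primary analysis does not depend on deviations. The documents do not give the number of patients affected; at ages 18 to 55, and with current users excluded, it is likely to be small. With approximately 60 subjects at approximately 40 sites (60 / 40 = 1.5 per site), many sites would have to interpret the text independently.

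The unlisted enrolment bar and the AT-527 reference are separate, smaller defects in the same part of the protocol. The conclusion assumes that the redacted text contains no precedence rule. No view is taken on which clinical rule is right.

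**What to change.** Reconcile the CYP3A4 paragraph of section 5.6.2 with exclusions 10 and 12 and section 5.6.1, so that one consistent instruction covers entry, use on study and restart for every drug named. State which section governs where they overlap, including whether methotrexate falls under the immunosuppressant entry. Make the section 5.6.2 enrolment condition consistent with the exclusion lists in section 4.2 and the synopsis. Reconcile the AT-527 reference in the P-gp inhibitor rule with the study drug. Which clinical rule applies in each case is for the sponsor's medical team.

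The cost is a few lines in a protocol amendment, with no new procedures, visits or patients.

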### Medical procedures

There are no specific medical procedures anticipated to impact evaluation of efficacy, safety or PK provided that the medical procedures 1) do not significantly alter the function of major organs involved in drug absorption, distribution, metabolism or elimination such as GI, liver

and kidneys; and 2) do not involve concomitant use of prohibited medications discussed above that may interfere with the PK AT-752.

## 6. STUDY ENDPOINTS

### 6.1 PRIMARY ENDPOINT

- Change in DENV viral load (DENV RNA as measured by RT-qPCR) from baseline

### 6.2 SECONDARY ENDPOINTS: PHARMACOKINETIC ENDPOINTS

- Plasma concentrations of AT-281 (and metabolites AT-551, AT-229, AT-219, and AT-273) for each cohort at the following timepoints:
  - Day 1: Pre-dose (before the first dose, time 0)
  - 24 hours after Dose 1 (before Dose 4 for TID dosing and before Dose 3 for BID dosing)
  - A day of intensive PK sampling:
    - i. For TID dosing, samples will be obtained before Dose 7 and 0.5, 1, 2, 4, and 6 hours after Dose 7. This serial PK sampling may be done for Dose 7, 8, or 9, based on site/patient convenience
    - ii. For BID dosing, samples will be obtained before Dose 5 and 0.5, 1, 2, 4, 6, and 8 hours after Dose 5. This serial PK sampling may be done for Dose 5, 6, or 7, based on site/patient convenience

For blood samples (both TID and BID dosing), a  $\pm 10$ -minute window for time points  $\leq 4$  hours;  $\pm 15$  minute for time points between 4 and 24 hours

  - At any early study discontinuation visits. The timing of these PK samples relative to the last 2 (most recent) doses will be recorded
- Noncompartmental analysis will be performed for the following plasma PK parameters, when applicable and if data permit. Other PK parameters may also be calculated. PK parameters, where applicable, will be calculated based on actual times:
  - $AUC_{last}$  (area under the plasma concentration versus time curve from time 0 to the last quantifiable concentration)
  - $AUC_{tau}$  (area under the plasma concentration versus time curve over the dosing interval)

- $AUC_{inf}$  (area under the plasma concentration versus time curve from time 0 to extrapolated to infinity)
- $C_{max}$
- $T_{max}$
- $t_{1/2z}$  (apparent terminal elimination half-life)
- CL/F for AT-281 only (apparent oral clearance)
- $V_z/F$  for AT-281 only (apparent volume of distribution)
- $C_{trough}$

### **6.3 SECONDARY ENDPOINTS: SAFETY ENDPOINTS**

- Incidence and grade of any TEAEs from first dose through Day 28 or withdrawal from the study
- Incidence and grade of any SAEs through Day 28 or withdrawal from the study
- Vital sign measurements
- Physical examination findings
- Clinical laboratory (serum chemistry, hematology, coagulation, and urinalysis findings)
- ECG findings

### **6.4 EXPLORATORY ENDPOINTS: PHARMACODYNAMIC ENDPOINTS**

- Change in DENV viral load (as measured by infectious viral titre) from baseline
- Area under the log10-transformed viral load curve (AUC) from first dose to the end of treatment or study (as measured by DENV RNA and viral titre)
- Time to viral load clearance, which is defined as the first of 2 consecutive undetectable viral load measurements (as measured by DENV RNA and viral titre)

- Time to clearance of NS1 protein using NS1 antigen test. Clearance is defined as time from start of treatment until the first of 2 consecutive plasma samples are NS1-negative.
- Change of DENV viral load (as measured by DENV RNA and viral titre) from baseline, viral load AUC, time to viral load or NS1 clearance by DENV serotype
- Treatment-emergent amino acid substitutions in DENV NS5 polymerase
- Time to resolution or duration of fever Exploratory biomarkers on immunological response to dengue (See list in [Section 8.3.4](#))
- Exploratory analyses may be performed to evaluate exposure-response relationship. The relationship between the exposure of AT-752 (and its metabolites) and DENV viral load may be explored using graphical displays

## 7. STUDY ASSESSMENTS

Before performing any study procedures, all potential subjects will sign an ICF as outlined in [Section 10.2.2.3](#). Subjects will undergo study procedures at the time points specified in the SOE ([Section 3](#)). The total amount of blood collected from each subject over the duration of the study, including any extra assessments that may be required, will not exceed 500 mL.

### 7.1 PHARMACOKINETIC ASSESSMENTS

PK plasma samples will be collected as described in [Section 6.2](#). For blood samples, there is a  $\pm 10$  minutes window for time points  $\leq 4$  hour and a  $\pm 15$  minutes window for time points between 4 and 24 hours.

Pharmacokinetic endpoints will be characterized as subject numbers and PK data permit.

#### 7.1.1 Pharmacokinetic Sample Collection

Details for the collection, processing, storage, and shipping of PK samples will be provided to the clinical sites in the study manual.

#### 7.1.2 Pharmacokinetic Sample Analysis

Pharmacokinetic samples will be analyzed using a validated liquid chromatography coupled with tandem mass spectrometry assays for AT-752 and metabolites AT-551, AT-229, AT-219

and AT-273 in human plasma. Assay results and validation details will be provided in a separate bioanalytical report.

## **7.2 PHARMACODYNAMIC ASSESSMENTS**

Temperature readings will be performed at least 4 times daily through the end of treatment (morning, mid-day, late afternoon, and evening; approximately every 4 hours during waking hours). Temperature will be measured orally and recorded in a patient diary (and given to the site coordinator for entry in the eCRF).

A rapid point of care (POC) test for DENV NS1 antigen and a DENV serotype test will be performed at screening. Viral load will be assessed by measuring plasma viremia by viral titre and with a serotype-specific, real-time reverse transcription PCR assay at screening and on Days 1-8, Day 14, and Day 28. DENV NS1 will be measured by ELISA at screening and on Days 1-8, Day 14, and Day 28. See [Section 3.1.4](#) for a description of the timing for collection of these samples.

## **7.3 SAFETY ASSESSMENTS**

Safety will be assessed by monitoring and recording of AEs, vital sign measurements, 12-lead ECG results, physical examination findings, and clinical laboratory test results (hematology, coagulation, serum chemistry, and urinalysis).

For all safety assessments, the investigator will determine whether results are clinically significant, which is defined as any variation in a result that has medical relevance and may result in an alteration in medical care (e.g., active observation, diagnostic measures, or therapeutic measures). If clinical significance is noted, the result and reason for significance will be documented and an AE reported on the AE page of the subject's eCRF. The investigator will monitor the subject until the result has reached the reference range or the result at screening, or until the investigator determines that follow-up is no longer medically necessary.

### **7.3.1 Adverse Events**

Adverse events will be assessed from the time of screening until EOS and should be followed until they are resolved, stable, or judged by the investigator to be not clinically significant.

The investigator is responsible for ensuring that all AEs and SAEs are recorded in the eCRF and reported to the sponsor, regardless of their relationship to study drug or clinical

significance. If there is any doubt as to whether a clinical observation is an AE, the event should be reported.

### 7.3.1.1 **Adverse Event Definitions**

An AE is defined as any untoward medical occurrence associated with the use of a drug in humans, whether or not considered drug related. Subjects will be instructed to contact the investigator at any time after randomization if any symptoms develop.

A treatment-emergent AE is defined as any event not present before exposure to study drug or any event already present that worsens in intensity or frequency after exposure.

A suspected adverse reaction is any AE for which there is a reasonable possibility that the study drug caused the AE. For the purposes of investigational new drug safety reporting, “reasonable possibility” means that there is evidence to suggest a causal relationship between the study drug and the AE. A suspected adverse reaction implies a lesser degree of certainty about causality than an adverse reaction.

An adverse reaction is any AE caused by a study drug. Adverse reactions belong to a subset of all suspected adverse reactions and indicate that there are reasons to conclude that the study drug caused the event.

An AE or suspected adverse reaction is considered “unexpected” if it is not listed in the investigator brochure or if it occurs with specificity or severity that has not been previously observed with the study drug being tested; or, if an investigator brochure is not required or available, the AE or suspected adverse reaction is not consistent with the risk information described in the general investigational plan or elsewhere in the current application. For example, under this definition, hepatic necrosis would be unexpected (by virtue of greater severity) if the investigator brochure referred only to elevated hepatic enzymes or hepatitis. Similarly, cerebral thromboembolism and cerebral vasculitis would be unexpected (by virtue of greater specificity) if the investigator brochure listed only cerebral vascular accidents. “Unexpected,” as used in this definition, also refers to AEs or suspected adverse reactions that are mentioned in the investigator brochure as occurring with a class of drugs or as anticipated from the pharmacological properties of the drug, but are not specifically mentioned as occurring with the particular drug under investigation.

An AE or suspected adverse reaction is considered an SAE/suspected unexpected serious adverse reaction if, in the view of either the investigator or sponsor, it results in any of the following outcomes:

- Death
- Life-threatening AE
- Inpatient hospitalization or prolongation of existing hospitalization
- Persistent or significant incapacity or substantial disruption of the ability to conduct normal life functions
- Congenital anomaly or birth defect

Important medical events that may not result in death, be life threatening, or require hospitalization may be considered serious when, based upon appropriate medical judgment, they may jeopardize the subject and may require medical or surgical intervention to prevent one of the outcomes listed in this definition. Examples of such medical events include allergic bronchospasm requiring intensive treatment in an emergency room or at home, blood dyscrasias or convulsions that do not result in inpatient hospitalization, or the development of drug dependency or drug abuse.

An AE or suspected adverse reaction is considered “life threatening” if, in the view of either the investigator or sponsor, its occurrence places the subject at immediate risk of death. It does not include an AE or suspected adverse reaction that might have caused death if it had been more severe.

